7.7.1. Primary Endpoint

The primary endpoint is the change in MDS-NMS total score at the end of the treatment period (day 113) relative to baseline (mean of day 0 and day 29) scores.

7.7.1.1. Statistical Significance

The null hypothesis is TNMTM Device treatments will yield an equivalent change in NMS burden in the two treatment arms. The alternative hypothesis is that the active treatment arm will do better than (be superior to) the passive treatment arm. The threshold to determine statistical significance will be set at $\alpha = 0.05$ based upon a 1-tailed test⁴.

7.7.1.2. Clinical Significance

Clinical significance is determined by how a treatment affects the extent to which a participant is currently living independent of help from others OR that there is a real genuine, palpable, and noticeable effect on daily life or how a patient feels, functions, or survives. Importantly, as the scores from the MDS-NMS are derived from the product of the symptom frequency (how often the participant has experienced a given non-motor symptom since the last evaluation with higher scores indicating more frequent experience) and the symptom severity (impact of that symptom on how the participant has felt and functioned with higher scores indicating greater distress or disturbance to patient or caregiver), reductions in MDS-NMS total scores are inherently clinically meaningful in that they represent how the participant is feeling and functioning. Given the inherent clinical meaningfulness of the MDS-NMS total scores, the primary endpoint will be considered clinically meaningful, and therefore, successful, if there is a statistically significant reduction in MDS-NMS total scores in the active tvCVS group relative to the passive treatment group after 12 weeks of twice-daily treatment.

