7.8.2.2. Clinical Significance

Clinical significance is defined by how a treatment affects the extent to which a subject is currently living independent of help from others OR that there is a real genuine, palpable, and noticeable effect on daily life or how a patient feels, functions, or survives. Importantly, as the scores from the MDS-NMS are derived from the product of the symptom frequency (how often the patient has experienced a given non-motor symptom since the last evaluation with higher scores indicating more frequent experience) and symptom severity (impact of that symptom on how the patient has felt and functioned with higher scores indicating greater distress or disturbance to patient or caregiver), reductions in MDS-NMS total scores are inherently clinically meaningful in that they indicate improvements in how the participant is feeling and functioning. Given the inherent clinical meaningfulness of the MDS-NMS total score, the primary endpoint will be considered clinically meaningful, and therefore, successful, if there are statistically significant reductions in MDS-NMS total scores after active tvCVS treatment during the OLE relative to the change in response to the 12 weeks of passive treatment during the RCT.

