4. SAMPLE SIZE DETERMINATION

The sample size for this study was set to achieve ~ 90% power to detect a minimal clinically important difference (MCID) of -2.64 points in the MDS-UPDRS: Part I (Horvath, Aschermann et al. 2017) for both the RCT and the first treatment period during the OLE. This estimated group sample sizes of 83 and 83 (166 total) to complete the RCT (assuming 10% attrition) achieves 89.2% power to detect a difference of 2.64 points in the MDS-UPDRS Part I total score for the null hypothesis that both group average change scores are equal and the alternative hypothesis that the average change score of the active treatment group represents greater symptomatic improvement than that of the passive treatment group given an estimated within group standard deviation of 5.32 points and a 2-sided significance level (alpha) of 0.05.

This sample size also achieves > 90% power to evaluate the primary endpoint of the STEM-PD OLE (see the STEM-PD OLE SAP for additional details).

Note that the primary outcome measure for the STEM-PD RCT is the MDS-NMS, not the MDS-UPDRS: Part I. However, the two scales are highly correlated (correlation coefficients = 0.75-0.85) (Chaudhuri, Schrag et al. 2019, van Wamelen, Martinez-Martin et al. 2021), and the MDS-UPDRS Part I has a pre-established MCID whereas the MDS-NMS does not. Given the high correlation reported for these two outcome measures in previous studies, an analysis was performed to estimate the MCID for the MDS-NMS. The MCID for the MDS-UPDRS: Part I is

2.64 points (Horvath, Aschermann et al. 2017). Since the estimated standard deviation of the MDS-UPDRS Part I for this study is 5.32 points, the MCID represents 49.6% of the standard deviation.

The standard deviation of the MDS-NMS scale has been reported as 65.87 points (Chaudhuri 2020). Using the same proportion of the standard deviation, the estimated MCID for the MDS-NMS scale for this study would be 32.7 points. Additionally, in an unpublished study analysis of participants from the original validation study, Martinez-Martin determined that among a cohort with MDS-UPDRS Part I scores greater than 10, which approximates the inclusion criterion for this study, the standard deviation of the MDS-NMS was 70.8 points. Utilizing a definition of 49.6% of the standard deviation, based upon the Martinez-Martin study, the MCID for the MDS-NMS scale would be 35.1 points.

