Further, Norman et. al., 2003 (Norman, Sloan et al. 2003) suggested that the MCID be defined as 50% of the standard deviation. Using the standard deviation of 65.87, the MDS-NMS MCID would be 32.9 points. As noted above, however, the proposed study requires subjects to have an MDS-UPDRS Part I score of at least 9 at the study screen. Therefore, utilizing the standard deviation of 70.8 points (Martinez-Martin, *unpublished*), the MDS-NMS MCID would be 35.4 points². As such, the estimated MCID range for improvement in the MDS-NMS for this Statistical Analysis Plan is -32.7 to -35.4 points. While these values provide estimates for sample size calculations, the MCID for the MDS-NMS from data collected within this study using methodology described in section 7.6.1.3.

Notably, the sample size (184 to randomize), derived from the MDS-UPDRS Part I also achieves 85.7% power to detect the estimated MCID minimum of -32.7 and 92.8% power to detect the estimated MCID maximum of -35 points in the MDS-NMS.

Competitive enrollment will be used. Participants will continue to be enrolled until at least 184 are randomized in the RCT, and if there are additional participant withdrawals, they will not be replaced. Any participant who had entered the baseline period but had not yet randomized when the competitive enrollment target is achieved may be withdrawn from the study prior to randomization, and as a result, will not be included in any of the analyses. Data from all randomized study participants will be evaluated for analyses of safety and efficacy. The protocol has planned for up to 290 study participants to be screened. The sample size of 184 to randomize allows for attrition of 10% in the RCT as well as attrition of 10% in the first treatment period of the OLE while still maintaining adequate power to evaluate the primary endpoints of those studies.

[figure not shown]

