7.7.2.3. MDS-UPDRS Part III

This endpoint will evaluate the change in MDS-UPDRS Part III score at the end of the treatment period (day 113) relative to the baseline (day 29) score. Changes will be considered to be clinically meaningful if the mean/median difference meets or exceeds the previously established MCID (-3.25 for clinical improvement) for this scale (Horvath, Aschermann et al. 2015).

This analysis will be derived only from the ON-state MDS-UPDRS Part III: motor exam scores, and MDS-UPDRS Part III data collected in the OFF-state will not be included in any analysis. The scores will be provided by blinded central raters when available except for scores from item 3 (related to rigidity). Scores for items related to rigidity will be derived from the blinded local rater scores when calculating the MDS-UPDRS part III score. Additionally, the ability of the centralized raters to provide scores will depend on the availability of quality video feed captured by the clinical sites. Video will be captured by Machine Medicine's Kelvin-PD software which was selected by the Sponsor to minimize the risk of video capture that is of inadequate quality for accurate centralized rating. However, it is possible that some video data may be missing or of poor quality, and thus, cannot be rated by a central rater. In cases where MDS-UPDRS Part III data from central raters from either the baseline or the end of treatment visit cannot be scored by the central rater, scores provided by the local raters will be utilized for both the baseline and end of treatment assessments. In cases where the last assessment was captured remotely using telemedicine platforms, the score will be prorated to the scale of the in-clinic MDS-UPDRS Part III. Additionally, the day 0 baseline measure (virtual visit) will be prorated to the scale of the in-clinic MDS-UPDRS Part III will be substituted for the baseline value. This will only occur if a virtual visit is required due to the participant's inability to travel to the site for the end of treatment visit.

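### Both SAPs treat a statistically significant primary endpoint as clinically meaningful by definition, which conflicts with the plan's own MCID checks and lets a difference of about half the planning MCID carry the clinical label.

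*SAP*

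**What the plan says.** RCT SAP 7.7.1.2 opens by describing clinical significance as an effect that is felt in daily life. It then reasons that, because MDS-NMS items multiply frequency by severity, any fall in the total score matters to the patient. It concludes that "the primary endpoint will be considered clinically meaningful, and therefore, successful, if there is a statistically significant reduction in MDS-NMS total scores" in the active group relative to the passive group. OLE SAP 7.8.2.2 does the same: "the primary endpoint will be considered clinically meaningful, and therefore, successful, if there are statistically significant reductions in MDS-NMS total scores" relative to the change under passive treatment. The test is at 0.05, "based upon a 1-tailed test" (RCT SAP 7.7.1.1). A footnote there adds one-tailed 0.025 for certain submissions.

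Elsewhere the plan treats size as a separate question:

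- RCT SAP 4: "the estimated MCID range for improvement in the MDS-NMS for this Statistical Analysis Plan is -32.7 to -35.4 points".
- RCT SAP 7.7.1.3: an MCID is derived from study data, responder rates are compared, and, if 36% or more of the passive arm respond, the mean or median difference is checked against the MCID. All of this is described as supplementary or supportive.
- OLE SAP 7.8.2.2.1 compares the OLE result with the RCT-derived MCID. OLE SAP 7.12.1.1 says that, with a passive responder rate of 36% or more, clinical significance is settled by whether the mean difference is larger than the MCID.
- Protocol 3.4.2 uses the NMS-focused CGI-I and the transition question to confirm the clinical significance of the primary endpoint.
- Secondary endpoints: for MDS-UPDRS Part III, "Changes will be considered to be clinically meaningful if the mean/median difference meets or exceeds the previously established MCID". Comparable MCID wording covers the combined MDS-UPDRS, Part II and PDQ-39SI. Overall CGI-I has no size criterion (RCT SAP 7.7.2.2, OLE SAP 7.8.4.3).

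**The concern.** That a scale measures how patients feel and function shows that it measures something relevant. It does not show that every detectable group difference on it is important. Under the rule, whether the result is called clinically meaningful depends on the estimate relative to its standard error, hence partly on sample size and SD, and not on the size of the effect alone.

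The rule can also disagree with the rest of the plan on the same data. Suppose the OLE comparison is significant, the mean difference is below the MCID, and the passive responder rate was 36% or more. OLE SAP 7.8.2.2 then declares the result clinically meaningful, while by OLE SAP 7.12.1.1 clinical significance is not established. Neither section says which prevails.

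The RCT is meant to support regulatory submissions, and the OLE is meant to support reimbursement and to confirm the clinical meaningfulness of the RCT results (Protocol 1.1.1 and 1.1.2). A headline clinical claim that the study's own MCID analysis contradicts would be hard to defend in either setting.

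**Working it through.** **Inputs.** 83 completers per arm, SD 5.32 for MDS-UPDRS Part I, MDS-NMS SDs of 65.87 and 70.8, and planning MCID 32.7 to 35.4 (all RCT SAP 4). One-tailed alpha 0.05, with 0.025 for some submissions (RCT SAP 7.7.1.1). 74 in the passive-active group (OLE SAP 4).

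**Reproducing the plan's figures.** The SAP states that the sample "achieves 89.2% power to detect a difference of 2.64 points in the MDS-UPDRS Part I total score", with "an estimated within group standard deviation of 5.32 points and a 2-sided significance level (alpha) of 0.05".

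- SE = 5.32 × √(2/83) = 0.826. Power = Φ(2.64/0.826 − 1.960) = Φ(1.237) = 0.892, as stated.
- MCID: 2.64/5.32 = 0.496. Then 0.496 × 65.87 = 32.7, 0.496 × 70.8 = 35.1 and 0.5 × 70.8 = 35.4. The range reproduces.
- MDS-NMS power at 35 points, SD 65.87: 0.928, as stated. At 32.7 points, SD 70.8: 0.845 against 85.7% stated. This small gap does not affect the point.

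**Smallest observed difference that is significant in the RCT**: t(1 − α, 164) × SD × √(2/83), where √(2/83) = 0.1552.

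| One-tailed α | SD 65.87 | SD 70.8 | Share of 32.7 to 35.4 |
|---|---|---|---|
| 0.05 (t = 1.654) | 16.9 | 18.2 | 48% (16.9/35.4) to 56% (18.2/32.7) |
| 0.025 (t = 1.975) | 20.2 | 21.7 | 57% (20.2/35.4) to 66% (21.7/32.7) |

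If the true difference were half the planning MCID (16.35 to 17.7 points), the chance of a significant result, and so of the clinical label, is about 44 to 53% at one-tailed 0.05.

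**If the study MCID falls back to 0.3 SD** (RCT SAP 7.7.1.3, used only when both anchor correlations are below 0.5): 0.3 × 65.87 = 19.8 and 0.3 × 70.8 = 21.2. At one-tailed 0.05 the ratio is 16.9/19.8, about 86% (85% with the normal quantile). At 0.025 it is 20.2/19.8 = 1.02, so there the smallest significant difference just exceeds the fallback MCID.

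**SD of change.** The documents give no SD for MDS-NMS change; the SDs above are those the plan itself uses for power. Assuming a change SD of 40 to 60, the threshold at one-tailed 0.05 is 10.3 to 15.4 points, or 29 to 47% of the planning MCID.

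**OLE.** The primary contrast is (day 197 − day 113) − (day 113 − day 29). The documents give no SD for it. Assuming equal variances and a common correlation r, its variance is 6(1 − r)σ², because day 113 enters twice. With σ = 65.87 and t(0.95, 73) = 1.666, so that 1.666/√74 = 0.1937:

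- r = 0.8: SD = 65.87 × √1.2 = 72.2; threshold 14.0 points (43% of 32.7).
- r = 0.6: SD = 65.87 × √2.4 = 102.0; threshold 19.8 points (60% of 32.7).

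These are simple two-group and paired approximations. The planned MMRM also fits visit and site, so its exact thresholds may differ somewhat.

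**The case against.** Much of the case on the other side stands.

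- **Size checks exist.** A reader might infer that the primary endpoint has no size criterion and is alone in that. The documents do not support this. OLE SAP 7.8.2.2.1 and 7.12.1.1 and RCT SAP 7.7.1.3 all compare the primary result with an MCID, and Overall CGI-I also has no threshold. What remains is that the primary-endpoint checks do not govern the declaration in 7.7.1.2 and 7.8.2.2.
- **The secondary contrast is about labels.** Success on the secondary endpoints is also decided by p-value in the hierarchy, and the MCID only labels the result. For the combined MDS-UPDRS score, the RCT text does not say whether the MCID applies to individuals, within arms or between arms.
- **A ratio near one half is generic.** For any design with about 89% power at two-sided 0.05, the one-tailed 0.05 critical value is 1.645/(1.960 + 1.237) = 51% of the design difference. The ratio is not a fault of this design. The fault is attaching a clinical label to it.
- **The planning MCID will be replaced.** The study value is unknown now, so the share against it may be higher or lower.
- **An individual-change MCID is not automatically a threshold for a mean difference.** The 7.7.1.3 value is a ROC cutoff on individual change. If the true effect equalled it, a pass/fail rule on the point estimate would fail about half the time. This limits the remedy, but the plan already compares mean differences with MCIDs, so the inconsistency is its own.
- **Readers will see the effect size.** The LS-mean difference with its interval, responder rates, number needed to treat and cumulative distribution are prespecified. They inform the reader but cannot overturn the declaration.

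**Conclusion.** The concern holds. Significance alone decides clinical meaning in RCT SAP 7.7.1.2 and OLE SAP 7.8.2.2, and this is not reconciled with the MCID checks elsewhere in the plan. In the RCT the label needs only about 17 to 18 points: 48 to 56% of the planning MCID at one-tailed 0.05, 57 to 66% at 0.025, and about 86% of the MCID under the 0.3-SD fallback. These figures rest on 83 per arm, the plan's scale-score SDs and a simple two-group comparison.

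The OLE threshold cannot be stated from the documents. Under the stated assumptions it is about 14 to 20 points. A reader might put SD 65.87 straight into a paired test and obtain 12.8 points, but that is a scale-score SD and not the SD of a difference of two change scores. It would require r of about 0.83.

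A reader might also infer that the primary test or its error rate is compromised. Nothing here supports that: the test, alpha and estimate are unchanged, and only the conclusion attached to them is at fault. A reader might further take the clinically-meaningful-change item among the RCT secondary objectives as referring to MDS-NMS. In Protocol 3.2 it occupies the same place in the list as CGI-I, so it should not be relied on. Severity: should-fix.

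**What to change.** 1. In RCT SAP 7.7.1.2 and OLE SAP 7.8.2.2, delete the sentences that equate significance with clinical meaning. Success under RCT SAP 7.7.1.1 and OLE SAP 7.8.2.1 is then a statistical conclusion only.
2. State that clinical meaningfulness is a separate conclusion, drawn from the LS-mean difference and its confidence interval set against the study MCID, together with the responder rates.
3. Bring RCT SAP 7.7.1.2 and 7.7.1.3, and OLE SAP 7.8.2.2, 7.8.2.2.1 and 7.12.1.1, into line, including the provision for a passive responder rate of 36% or more. OLE SAP 7.8.2.2.1 should also say which quantity is compared with the MCID: it refers first to the difference between treatments and then to the mean change on active treatment.
4. If these results do not support importance, report *statistically significant, clinical importance not established*.

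A hard rule that the point estimate must reach the MCID is not required, for the reason given above.

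The cost is wording; the component analyses are already planned. The change should be made before unblinded results are seen. The downside is that the sponsor may win statistically without a clinical-meaning claim.

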7.7.1.3. Supportive analysis to further explore clinical significance

The structure and methodology for data collection of the MDS-NMS allows for statistically significant changes to be interpreted as inherently clinically meaningful. However, the scale is relatively new and may not be well known by all prescribing/referring physicians. Therefore, to facilitate clinical adoption, a supplementary analysis will be performed that establishes a minimal clinically important difference (MCID) for the MDS-NMS within the study. The MCID will be defined using an anchor-based approach and will be defined as the average of the

⁴ Regulatory review within certain bodies (e.g., the United Kingdom) may require that the endpoint results meet a threshold with an alpha of 0.025 based upon a 1-tailed test. Therefore, this higher level of significance will also be evaluated for certain premarket submissions.

MCIDs estimated from a compilation of data from both the intervention (active treatment) and the control (passive treatment) arms for two distinct anchors.

These anchors include (1) the Non-Motor Symptom-focused Clinical Global Impressions Scale – Improvement (NMS CGI-I), part of the Focused CGI-I, and (2) the Non-Motor Symptom Burden transition question (Transition Questionnaire). The NMS CGI-I is a clinician-rated scale that is based on account information gathered through interviews with the study participant and the study partner and through the review of medical records. The NMS CGI-I will evaluate clinically meaningful change between the baseline and the end of the treatment period. The Non-Motor Symptom Burden question (Transition Questionnaire) will capture participant reports of perceived change in overall NMS burden after four weeks of treatment compared to the period before starting treatment with the device.

These two anchors will be collected at the same study visits or on the ePRO data collection associated with the MDS-NMS data collection on Treatment Visit 1 (day 57). This data collection will allow for sufficient power to calculate the receiver operating characteristic curve (ROC) with 95% confidence and 80% Power (Figure 2). Spearman correlation coefficients will then be calculated to determine, separately, the relationship between each of these measures and changes in the MDS-NMS score. Assuming that both measures show correlation coefficient with magnitude of at least 0.5, the following steps will be undertaken. ROC curves will be developed separately determine for each of the measures to cutoff values that best define the MCID calculated with that anchor (Kumar and Indrayan 2011). Note that for NMS-focused CGI-I, the standard approach of utilizing ROC analysis to determine the optimal cutoff value in the MDS-NMS Total Score that best distinguishes 'minimally improved' (score of 3) from 'no change' (score of 4) (Hauser, Auinger et al. 2011, Horvath, Aschermann et al. 2015, Falissard, Sapin et al. 2016, Czobor, Sebe et al. 2022, Christensen, Adair et al. 2023) will be performed. For the Non-Motor Symptom Burden transition question (Transition Questionnaire), the ROC will be developed to calculate the cutoff value in the MDS-NMS Total Score that best distinguishes 'mildly better' from 'no change'. For each measure, because the risks of false positive and false negative may not be equal, Youden's J statistic will be used to determine the MCID (Youden 1950)

$$\mathbf{J} = \frac{ad - bc}{(a+b)(c+d)}$$

and a, b, c, and d are subject counts defined from:

		Based on	Measure
		Improving	Not improving
	Improving	а	b
Based on Anchor	Not Improving	С	d

The largest J statistic value for both ROC curves will define the MCIDs for each of the two anchors (i.e., the NMS CGI-I and the Non-Motor Symptom Burden transition questionnaire).

Having now obtained two separate estimates for the MCID, the weighted average, where the correlation squared (r^2) value will be the associated weight, will then be utilized to determine the operationalized MCID. If exactly one of the two Spearman correlation coefficients previously calculated to determine relationships between each measure and the change in the MDS-NMS score has a magnitude below 0.5, then that measure will be disregarded, and the MCID will be determined solely for the measure that had correlation coefficient of at least 0.5. Lastly, if both of the Spearman correlation coefficients have magnitudes below 0.5, then a distribution-based approach will be utilized to determine the MCID. The distribution-based method would be performed wherein the distribution of MDS-NMS Total Scores at baseline are used to determine the standard deviation of the baseline scores. This value is then multiplied by 0.3 to determine the MCID as 0.3 is defined as a small effect size (Anderson, Kelley et al. 2017). To support the conclusions of this distribution-based method of defining the MCID, a correlation analysis evaluating changes in the MDS-NMS and the MDS-UPDRS Part I may also be conducted as the latter is known to strongly correlate with the MDS-NMS and has a previously established MCID of 2.64 points (Horvath, Aschermann et al. 2017).

[figure not shown]

Figure 2: Sample size requirements for ROC curve analysis. Note: It is expected that the area under the ROC curve (AUC) will have a value between 0.65 and 0.75.

Once the MCID is determined, it can be used to calculate the percentage of cases that exceed that value for each of the two treatment arms (i.e., responder rates). To further support clinical adoption, a supporting Fisher's exact test analysis will be employed to determine if the responder rate for active treatment participants is statistically significantly greater than the response rate for passive treatment participants. For statistical significance, the required percentage of participants in the intervention group that demonstrate a change exceeding the MCID will be a function of the percentage of participants in the passive treatment group that demonstrate a change exceeding the MCID. This relationship is depicted in Figure 3. Because the power of this binomial comparison will be reduced under conditions where there is a high rate of passive treatment participants that exceed the MCID, if 36% or more of the passive treatment arm exceeds the MCID (a condition that would require > 60% responder rate in the active arm), clinical significance for the primary outcome measure will instead be further supported by verifying that the mean/median difference between the two treatment arms exceeds the change equivalent to the MCID.

[figure not shown]

Figure 3: Effect of Percent in Passive Group Exceeding MCID on the Required Percent of Active Group Needing to Exceed MCID to demonstrate statistical significance using binomial comparison.

Additional analyses of the primary endpoint measure to support clinical adoption will include the following:

• The percent change of scores (normalized to the average baseline)

The percent change of scores is calculated as the mean change score divided by the mean baseline value multiplied by 100.

• The percentage of participants who improved by 1 MCID or more (i.e., change from baseline in MDS-NMS Total Score at Day 113 ≥ MCID calculated on an individual level). Participants who do not meet this criterion are non-responders.

The proportion of participants whose change from baseline to Day 113 in NMS-MDS total score met or exceeded the MCID will be summarized by treatment group.

• Effect Sizes

Effect size will be calculated in two ways:

- a. Cohen's w will be calculated for the 2x2 table of responders/non-responders and treatment group. Cohen's w is calculated as the square root of the chisquare test statistic divided by the total number of participants. Responders are defined as those participants with change from baseline in MDS-NMS Total Score at Day 113 ≥1 MCID. Non-responders are those who did not respond (includes missing data as non-responders).
- b. Cohen's D will be derived as the ratio of the estimated difference in the change from baseline MDS-NMS to the population standard deviation at each visit estimated from the model (the square root of the diagonal elements of the estimated covariance matrix).
- The number needed to treat to obtain 1 patient with improvement of 1 MCID or more

The number needed to treat is calculated as 1/the absolute difference between treatment groups in the proportion of non-responders (i.e., change from baseline in MDS-NMS Total Score at Day 113 < MCID or missing).

• Reliable Change Index

Reliable Change Index is defined per participant as the difference of the pre and post treatment scores divided by the standard error of the measurement. The standard error of the measurement is calculated as the square root of two times the standard error of the mean difference between pre and post treatment scores, squared ($\sqrt{2(\text{SEM}^2)}$). This value is compared to the cutoff score assuming a normal distribution and 95% confidence level. The proportion of values above (RC+), below (RC-), and at (RCo) the cutoff value will be presented. This value will be calculated for the change from baseline in MDS-NMS Total scores at Day 113.

• Cumulative Distribution Plot

A plot of the cumulative distribution of the change from baseline in MDS-NMS Total scores at Day 113 will be prepared.

